Secondary Study Objectives	
The secondary objectives of this study are to:
 
 1) Compare total plaque volumes per-patient and per lesion as well as comparing different plaque type volumes to the IVUS reference standard and assess reproducibility of quantitative plaque measurements compared to the reference standard. 2) Perform exploratory analyses on plaque in previously stented vessels (protocol to allow up to 20% (50 patients) with one or two stented vessels vessels in this category. This can also include plaque proximal or distal to the stented vessel.
Hypotheses	The primary hypothesis of the study is that a deep-learning based automated method for segmenting coronary atherosclerotic plaques can quantify total plaque volume from CCTA with an acceptable level of agreement with IVUS measurements. The secondary hypothesis of the study is that CCTA-derived coronary models can accurately assess percent plaque burden as well as calcified, low attenuation, and fibrous plaque volumes with an acceptable level of agreement and repeatability compared to IVUS.
Population	Clinically stable patients with known CAD who have a CCTA showing stenosis in at least one major epicardial vessel of stentable/graftable diameter and in whom clinically-indicated IVUS is planned.
Study Design and Methods	This is a prospective, multi-center study. All patients who have a stenosis in at least one major epicardial vessel confirmed by CCTA, who have undergone FFR _{CT} analysis, and who are scheduled to undergo clinically indicated IVUS-guided invasive evaluation and/or treatment will be eligible for enrollment. Enrolling sites will have FFR _{CT} analysis incorporated when indicated into their standard evaluation of CCTA scans. Data collected will include CCTA and FFR _{CT} , full angiographic, and IVUS images, and if obtained, any other imaging or physiologic data including OCT, FFR, any NHPR (e.g., dPR, RFR, iFR, etc.), and pre-

REVEALPLAQUE Study Protocol Version 1.0 August 12th, 2021

	
and post-stent implantation invasive data. All non-invasive and invasive data collected will be obtained as clinical practice consistent with standard clinical care.
 
All details about cardiovascular testing and treatment (planned and actual) will be recorded at baseline. There will be no study required visits after the baseline invasive procedure.

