1. Compare total plaque volumes per-patient and per lesion as well as comparing different plaque type volumes to the IVUS reference standard and assess reproducibility of quantitative plaque measurements compared to the reference standard.
2. Perform exploratory analyses on plaque in previously stented vessels (protocol to allow up to 20% (50 patients) with one or two stented vessels in this category). This can also include

REVEALPLAQUE Study Protocol Version 1.0 August 12th, 2021

plaque proximal or distal to the stented vessel.

III. STUDY ENDPOINTS

III. A. Primary Endpoint

The primary endpoint is to assess the level of agreement between total plaque volume of a deep-learning based automated method for segmenting coronary atherosclerotic plaques, compared to IVUS, on a per-IVUS-pullback level.

III. B. Secondary Endpoints

Key secondary endpoints are:

Per pullback:

- Total plaque volume
- Percent plaque burden
- Calcified plaque volume
- Low attenuation plaque volume
- Fibrous plaque volume
- Segment involvement score (SIS)
- Adverse plaque characteristics (APC)

Per lesion:

- Total plaque volume
- Percent Plaque burden
- Calcified plaque volume
- Low attenuation plaque volume
- Fibrous plaque volume
- Minimum lumen area (MLA)
- Percentage area stenosis (%AS)
- Positive remodeling index

Per lesion/pullback:

- Reproducibility of all metrics above when quantified from different CCTA series
- Reproducibility of all metrics above when processing the same series twice (analyst and process variation)
- Exploratory analysis of necrotic core volume

IV. STUDY DESIGN

The REVEALPLAQUE study is a prospective, multi-center study designed to evaluate a deep-learning based automated method for segmenting coronary atherosclerotic plaques. All patients who have a stenosis confirmed by CCTA and FFR_{CT} available and who are scheduled to undergo IVUS will be eligible for enrollment. Enrolling sites will have FFR_{CT} analysis incorporated when indicated into their standard evaluation of CCTA scans. All sites will provide CCTA and FFR_{CT} images, full angiographic images, IVUS images, and if obtained, any other imaging or physiologic data including OCT, FFR, any NHPR (e.g., dPR, RFR, iFR, etc.), and pre- and post-stent implantation invasive data. All non-invasive and invasive data collected will be obtained as clinical practice consistent with standard clinical care.

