Subjects included in the study will have anatomic and physiological data obtained as standard clinical care during ICA recorded. A guide advising how to obtain IVUS measurements will be provided to sites during site protocol training; in summary the below mentioned data will be collected. A maximum of 20% of enrolled subjects may have at least one vessel with prior stent implantation.

ICA procedure:

1. The subject's vital signs (blood pressure and heart rate) will be recorded prior to ICA procedure.
2. Medications (adenosine and nitrates) taken within 24 hours of ICA will be recorded.
3. Angiography is advised to be performed according to the study guides provided during site protocol training.
4. The data from IVUS (mandatory), FFR measurements (as deemed necessary), and OCT (as deemed necessary) by the physician will be collected.
5. All angiographic images will be collected.
6. IVUS data for non-targeted lesions that are standard clinical care will be collected.
7. Radiation exposure will be documented.
8. Total procedural volume of iodinated contrast will be recorded
9. Fluoroscopy duration will be documented.
10. Diagnostic and therapeutic procedures and equipment used, including catheters, balloons, wires, and stents, and vessels treated will be documented.

REVEALPLAQUE Study Protocol Version 1.0 August 12th, 2021

11. Procedural complications will be documented (e.g., dissection from catheter or wire, reaction to medication, side branch occlusion, slow/no flow)

V. E. Follow up

No follow up with the subjects will be done as a part of this study.

VI. STUDY DURATION

The anticipated enrollment duration of the REVEALPLAQUE study will be approximately 12 months. No subject follow up is planned for this study.

VI. A. Rules for Subject Withdrawal

Each subject is free to withdraw from the study at any time. No additional data will be collected after a subject informs the Investigator that they want to withdraw. Withdrawn subjects will be considered screen failures if the collected data does not allow for adequate selection criteria assessment.

VI. B. Screen Failures

Subjects who sign consent will be deemed a screen failure if:

- Automatic pullback for IVUS catheter was not used during the procedure
- Prior to IVUS, the vessel was predilated (medications OK)

No data beyond reason for screen failure will be collected.

VI. C. Rules for Terminating the Study

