measures will be assumed to agree. Additionally, Pearson's correlation and paired t-test will be constructed to further describe the relationship between IVUS measurements and deep-learning based automated method for segmenting coronary atherosclerotic plaques from CCTA.

All secondary endpoints which are continuous (e.g., per lesion total plaque volume, per lesion calcium volume, per lesion low attenuation volume, per lesion non-calcified plaque volume, segment involvement score) will be similarly compared using a Bland Altman plot, Pearson's correlation and paired t-tests. Reproducibility will be estimated with Intra Class correlation (ICC).

IX. D. Sample Size

Approximately 250 subjects may be enrolled into this study.

From published data (Conte 2019), the maximum allowable difference between the measurements is 36 mm³. Assuming a standard deviation of 12 mm³, a sample size of 223 patients achieves 90% power to detect agreement when the mean is 8, confidence level of the (LoA) is 0.950 and the confidence level of the confidence intervals about the LoA is 0.950.

IX. E. Analysis Populations

All subjects who meet the study criteria, sign the written informed consent, and are enrolled in the study, and provide paired assessments of CCTA and IVUS measurements will be included in the analysis set.

X. DATA HANDLING AND QUALITY ASSURANCE

X. A. Completing and Signing Case Report Forms

This study will utilize eCRFs for the collection of all data. Data changes and corrections for any errors should be corrected within the eCRF. The audit trail will record all changes made, the date and time of the correction, the person making the change, and a reason for the change. The appropriate electronic signature will be provided by the investigator as indicated.

X. B. Clinical Data Management

The sponsor or designee will be responsible for the processing and quality control of the data. The handling of data, including data quality control, will comply with all applicable regulatory guidelines.

The training of clinical site personnel in eCRF completion will be the responsibility of the sponsor or designee. To ensure uniform data collection, Case Report Form Guidelines will be created to assist with eCRF completion. All site staff including investigators and research coordinators will undergo site initiation training to become thoroughly familiar with the protocol, case report forms, and with methods of data verification.

X. C. Archiving of Data

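### Does the plan need to say whether pullbacks from previously stented vessels enter the primary limits of agreement?

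*Combined protocol and SAP*

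**What the plan says.** Secondary Objective 2 in Section II, repeated in the Synopsis, intends to "Perform exploratory analyses on plaque in previously stented vessels (protocol to allow up to 20% (50 patients", and adds: "This can also include plaque proximal or distal to the stented vessel". Section V.D sets the cap at enrolment: "A maximum of 20% of enrolled subjects may have at least one vessel with prior stent implantation". Section IV.C excludes prior PCI in three or more vessels, so patients with one or two treated vessels are eligible.

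The primary endpoint (III.A, IX.C) is agreement in total plaque volume at the level of the IVUS pullback, with no condition on stents. Section IX.E gives the only analysis set: subjects who are eligible, consented and enrolled and who "provide paired assessments of CCTA and IVUS measurements will be included in the analysis set".

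Section IX.D states "Approximately 250 subjects may be enrolled into this study" and, for a maximum allowable difference of 36 mm³ and an SD of 12 mm³, that "a sample size of 223 patients achieves 90% power to detect agreement when the mean is 8".

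The screen-failure rules in VI.B concern the conduct of the IVUS procedure (for example, "Automatic pullback for IVUS catheter was not used during the procedure", or predilation beforehand) and do not mention stents. Section IX.A describes Section IX as a brief overview and leaves the methods to a SAP. Sections XI.F and XI.G leave image-handling detail to core-lab workflows and study manuals.

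**The concern.** The analysis set is defined by subject, but the endpoint is measured by pullback. One patient may supply a pullback through a stented vessel and another through a native one, so a subject-level rule does not say outright which pullbacks count. Secondary Objective 2 gives stented-vessel plaque its own exploratory analysis and its own cap, which could be read as setting those vessels apart from the primary analysis.

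The cap (50 patients, 20%) is also larger than the margin between enrolment and the required number (27 patients, 10.8%). On the separate reading, a study that enrols 250 could fall short of 223 and lose its stated power. If the choice were still open once data were available, the sponsor would have two sets on which agreement could be declared.

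**Working it through.** **Inputs (IX.D unless noted).** Maximum allowable difference 36; mean difference 8; SD 12; limits of agreement at 95%; confidence intervals about the limits at 95%; required n = 223; enrolment about 250; stented allowance up to 50 (Secondary Objective 2).

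**Formula.** The standard error of a limit of agreement is SE = SD × √(1/n + z²/(2(n−1))), with z = 1.96. Agreement requires the outer 95% confidence bounds of both limits to lie within ±36. Power comes from the non-central t distribution with n−1 degrees of freedom. The non-centrality is (36 − 8 − 1.96×12)/SE = 4.48/SE for the upper limit and (36 + 8 − 1.96×12)/SE = 20.48/SE for the lower. The lower limit is never binding here.

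**Reproducing 223.** At n = 223, SE = 12 × √(1/223 + 3.8415/444) = 1.375 and the upper non-centrality is 4.48/1.375 = 3.26. Power is 0.9004; at n = 222 it is 0.8991. So 223 is the smallest n with 90% power, and IX.D's method is identified.

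**Power for each reading (one pullback per patient, same bias and SD in all vessels).**

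| Patients in the primary analysis | SE | Upper non-centrality | Power |
|---|---|---|---|
| 250: all included | 1.299 | 3.45 | 0.930 |
| 225: 25 stented set aside (half the cap) | 1.369 | 3.27 | 0.903 |
| 223: planned | 1.375 | 3.26 | 0.900 |
| 200: 50 stented set aside (full cap) | 1.453 | 3.08 | 0.866 |

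**Where the shortfall begins.** 250 − 223 = 27. Setting stented vessels aside misses the target only when more than 27 patients have no unstented-vessel pullback. Reaching 200 needs two things together: all 50 places filled, and none of those patients supplying a pullback from another vessel. The first is a ceiling, not a target. The second is not assured, because V.D provides that "IVUS data for non-targeted lesions that are standard clinical care will be collected".

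**Which reading the text supports.** IX.E names one set and admits every enrolled, eligible subject with paired data. The endpoint carries no stent restriction, eligibility admits one or two treated vessels, and no section excludes a stented vessel from the primary analysis. The separate reading is inferred only from the exploratory label and the cap. The plan already analyses overlapping parts of the same data: its per-lesion endpoints sit inside the per-pullback set without taking anything out of it.

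**The case for a change.** The strongest case for a change is that the gap is real at pullback level. IX.E cannot assign a vessel, and no rule covers a pullback that crosses both a stent and native plaque. The stented allowance exceeds the sample-size margin, and a sentence or two would close the matter at no cost. Simulation adds to this. With 200 unstented and 50 stented patients at the planning inputs, the two sets give opposite verdicts in about 8.9% of studies (5.0% with 25 stented). With the true upper limit exactly at 36, false agreement rises from about 3.4% to 4.8% if the more favourable set may be picked afterwards.

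The silence on pullbacks stands, and so does the arithmetic. The rest carries less weight. The simulations judge agreement by confidence bounds inside ±36, which IX.D implies. The rule written in IX.C is different: it asks whether CCTA measurements fall within limits estimated from IVUS. The simulations also assume equal bias and SD in all vessels, so the 8.9% is what dropping any 50 of 250 patients at random would produce. The documents give no evidence that agreement differs in stented vessels. The scope for choosing afterwards depends on the SAP, workflows and manuals being silent as well, which cannot be shown from the protocol. Finally, the remedy would only record a choice that is defensible either way.

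**Conclusion.** No change is needed. Followed as written, IX.E includes all subjects with paired data, and 250 evaluable patients give about 93% power against the planned 90%. If stented-vessel pullbacks were set aside, the 223 would still be met with up to 27 patients lost. The extreme case of 200 patients costs about 3.4 points (90.0% to 86.6%).

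These figures rest on IX.D's mean and SD, one pullback per patient, equal agreement in stented and native vessels, and no other loss of paired data. Missing pairs would lower power under either reading: with 223 evaluable patients, keeping everyone gives 90.0%, and removing a 20% stented share leaves 178 and 82.5%. The low figure again needs the full cap and a reading that the text does not adopt.

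How stented and mixed pullbacks are handled is a detail that an analyst would ordinarily settle in the SAP before analysis, with the other choice as a natural sensitivity analysis.

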HeartFlow will identify and qualify the clinical research sites for the REVEALPLAQUE study. Participating sites will be screened for:

- CCTA acquisition practices conforming to SCCT guidelines
- Invasive Coronary Angiography (ICA) and other invasive data collection following best practices
- High quality IVUS data collection experience and ability to use automatic pullback for IVUS

REVEALPLAQUE Study Protocol Version 1.0 August 12th, 2021

- Adequate resources and past clinical research experience

V. B. Subject Selection

Institutional Review Board (IRB) approval will be obtained at all participating sites prior to screening subjects. All subjects who meet all inclusion criteria and do not meet any exclusion criteria, and are able and willing to participate, are candidates for the REVEALPLAQUE study. All subjects providing written informed consent and meeting all selection criteria will be enrolled into the REVEALPLAQUE study.

V. C. Screening Period

1. All subjects must fulfill all study inclusion criteria and no study exclusion criteria.
2. Each subject will undergo the following assessments to be documented in the appropriate electronic case report form (eCRF) upon enrollment:
 - a. Collection of demographic information
 - b. A summary of the subject's relevant medical history and cardiovascular risk factors
 - c. Information about the subject's CCTA and FFR_{CT} results
 - d. Results and images from non-invasive/invasive tests performed during 90 days prior to enrollment

V. D. Enrollment

All subjects must provide written informed consent prior to enrollment. A notation will be made in the subject's medical chart, if required by the institution, and in the study records that he/she is participating in the study, has had his/her questions answered, has read, signed, and dated the Informed Consent Form (ICF), and been given a copy of the ICF.

All subjects who meet eligibility requirements will be asked to participate. Subjects will be considered enrolled in the study after the following criteria have been met:

1. Informed consent form has been signed and subject has been provided a copy.
2. All inclusion criteria and no exclusion criteria have been met.

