The REVEALPLAQUE study is a prospective study which collects data from clinically indicated CCTA imaging and ICA procedures. These procedures will have been planned as part of routine clinical practice; therefore, no additional clinical risks are related to participating in the study. Procedural complications will be documented that are related to IVUS or FFR (e.g., dissection from catheter or wire, reaction to medication).

IX. STATISTICAL CONSIDERATIONS**IX. A. General Considerations**

Descriptive statistical methods will be used to summarize the data from this study, with confidence intervals and hypothesis testing performed for the primary and other selected efficacy endpoints. Unless stated otherwise, the term “descriptive statistics” refers to number of events (n), mean, median, standard deviation (SD), standard error, minimum, maximum, and coefficient of variation (CV) for continuous data and frequencies and percentages for categorical data.

All data collected during the study will be included in data listings.

Unless specified otherwise, all statistical testing will be two-sided and will be performed using an overall significance (alpha) level of 0.05.

All statistical analyses will be conducted with the SAS® System, version 9.1.3 or higher.

A statistical analysis plan (SAP) will describe the methods of data collection, validation, analysis, and reporting. The sections below provide a brief overview of statistical consideration for the study.

IX. B. Subject Characteristics

Subject accountability will be described, including number of subjects enrolled, number of subjects included in the analysis, and reasons for any subjects discontinued from the study or not included in the analysis. Demographic information will be summarized using descriptive statistics. Sex and medical histories will be summarized by counts and percentages.

IX. C. Endpoint Analysis

The primary endpoint is to assess the level of agreement between total plaque volume of a deep-learning based automated method for segmenting coronary atherosclerotic plaques, compared to IVUS, on a per-IVUS-pullback level.

Bland Altman plots will be constructed. If the deep-learning based automated method CCTA measurements fall with the limits of agreement (LoA) estimated from the IVUS measurements, the

REVEALPLAQUE Study Protocol Version 1.0 August 12th, 2021

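### The screen-failure rule in VI.B excludes whole subjects although the primary endpoint is per pullback, and it conflicts with the data V.C records at enrolment

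*Combined protocol and SAP*

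**What the plan says.** - **VI.B, Screen Failures.** The rule acts on people: "Subjects who sign consent will be deemed a screen failure if" either of two things happened. One is "Automatic pullback for IVUS catheter was not used during the procedure". The other is "Prior to IVUS, the vessel was predilated (medications OK". It closes with "No data beyond reason for screen failure will be collected". It does not say which vessel is meant when several are imaged, and no pullback-level exclusion appears anywhere.
- **III.A and IX.C, primary endpoint.** Agreement in total plaque volume is assessed "on a per-IVUS-pullback level".
- **V.D, ICA procedure, item 6.** "IVUS data for non-targeted lesions that are standard clinical care will be collected", so more than one pullback per subject is foreseen.
- **V.D, Enrollment.** A subject counts as enrolled once consent is signed and eligibility is met. Both VI.B triggers arise later, at the invasive procedure.
- **V.C, Screening Period.** "Each subject will undergo the following assessments to be documented in the appropriate electronic case report form (eCRF) upon enrollment". The list covers demographics, medical history and risk factors, CCTA and FFRCT results, and earlier tests.
- **IX.B and IX.E.** Reasons for leaving subjects out of the analysis are to be reported. The analysis set is enrolled subjects with paired CCTA and IVUS measurements.

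**The concern.** The unit of exclusion does not match the unit of analysis. A subject with one predilated vessel and one untouched vessel imaged by automatic pullback has a valid observation for the primary endpoint. VI.B, followed to the letter, removes it. IX.E would admit the same subject, who is enrolled and has a paired measurement. Sites and the core lab could therefore apply the rule differently.

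The second problem is what remains on record. These are exclusions after enrolment, caused by events at the procedure. The count and the reason will be visible. What is not assured is any description of the excluded subjects, because VI.B limits collection to the reason while V.C has already called for baseline and CCTA/FFRCT data. If predilated vessels tend to hold tighter or more calcified disease, the analysed set would differ from the eligible population. That tendency is an assumption, and only retained baseline data would let anyone check it.

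**Working it through.** **1. The plan's own figure.** IX.D gives a maximum allowable difference of 36 mm³, mean difference 8, SD 12, 95% limits of agreement, 95% confidence intervals about them, and 223 patients for 90% power. I used the non-central t calculation for the intervals about both limits:

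- SE = SD × √(1/n + 1.96²/(2(n−1))). At n = 223 this is 1.375.
- Noncentralities: (36 − 8 − 1.96×12)/SE = 3.26 and (36 + 8 − 1.96×12)/SE = 14.89.
- Power = 1 − (β₁ + β₂) = 0.900 at two-sided 0.05. The smallest n reaching 0.90 is 223, so the stated figure reproduces exactly.

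**2. Pullbacks lost under the subject-level rule.** The documents give no rates, so these inputs are assumptions: m is the share of subjects with two imaged vessels (20-40%, the rest having one), and q is the chance that a vessel fails (5-15%), independent between vessels. With 250 subjects:

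- kept under a pullback-level rule: 250(1+m)(1−q)
- kept under VI.B read literally: 250[(1−m)(1−q) + 2m(1−q)²]
- difference: 250 × 2mq(1−q)

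| m, q | Kept, pullback rule | Kept, VI.B | Lost |
|---|---|---|---|
| 0.20, 0.05 | 285.0 | 280.25 | 4.75 |
| 0.30, 0.10 | 292.5 | 279.0 | 13.5 |
| 0.40, 0.15 | 297.5 | 272.0 | 25.5 |

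At these rates the losses are upper figures. They apply both triggers vessel by vessel, and positive correlation between a subject's vessels would reduce the number with exactly one failed vessel.

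**3. Effect on power.**

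- *Subjects as the unit.* The number with at least one usable pullback is 250[(1−m)(1−q) + m(1−q²)] under a pullback rule, against 250[(1−m)(1−q) + m(1−q)²] under VI.B. In the middle case this falls from 232 to 218 (power 0.911 to 0.894). In the most severe case it falls from 225 to 200 (0.903 to 0.866).
- *Pullbacks as the unit.* VI.B still leaves 272 to 280 pullbacks. Treated as independent, these give power of about 0.95.
- *In between.* With an assumed within-subject correlation of 0.5, the most severe case has 250×0.60×0.85 = 127.5 one-vessel subjects and 250×0.40×0.85² = 72.25 two-vessel subjects. The rough effective number is 127.5 + 72.25×2/1.5 = 223.8, with power about 0.90.

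**4. The text side by side.** Under V.D the subject is enrolled. Under V.C the baseline and CCTA/FFRCT data are recorded at that point. The trigger then occurs at the procedure, and VI.B says only the reason is collected. IX.E looks only at enrolment and paired data. Nothing states which section governs.

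**The case against.** The strongest reply is that the rule is sound in substance and only loosely worded. Predilation changes the vessel before the reference measurement, so that pullback should not be used. That stands, and the point here does not dispute it.

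Other parts of the reply also stand:

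- The vessel in VI.B can be read as the one imaged by the pullback in question. The automatic-pullback trigger speaks of the procedure as a whole, so a subject with one valid automatic pullback need not fail it. Predilation is then the only clear route to the loss.
- The reason for failure is kept, and IX.B requires reasons for exclusion to be reported. VI.B does not say that data already recorded are deleted. A reader might infer that nothing is kept or that baseline data are discarded; the text supports only an unresolved conflict with V.C.
- A reader might treat the gap between 250 and 223 as an allowance that these exclusions use up. IX.D does not call it one, and the protocol does not say whether screen failures count towards 250 or are replaced.
- Under XI.G the study plaque volumes are derived only after core-lab annotation. A subject without a valid pullback would have no matched CCTA plaque volume, so any comparison has to rest on data recorded at enrolment.

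The reply does not remove the mismatch between a subject-level exclusion and a pullback-level endpoint, or the conflicts with V.C and IX.E.

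**Conclusion.** The point holds as a mismatch of unit and a conflict between sections. VI.B read literally loses valid pullbacks, and V.C, V.D, VI.B and IX.E do not fit together for a subject who meets a trigger at the procedure.

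The size is modest and cannot be fixed from the documents. Under the assumed rates it is at most about 5 to 26 pullbacks per 250 subjects. Power falls below 0.90 only if subjects are counted and second pullbacks are given no weight, and even then the lowest value is 0.866.

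Two stronger readings are not supported. A reader might infer that the rule selects away from tight, calcified or hard-to-cross lesions. The documents say nothing about why or how often vessels are predilated, or whether agreement is worse there, so this remains an assumption to be checked. A reader might also infer that leaving out such vessels makes the planned power misleading. A corrected rule would still exclude predilated pullbacks, so on that account the variability of the analysed data would be no different.

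**What to change.** - **VI.B:** state the data exclusion per vessel and pullback. A pullback is left out if that vessel was predilated before IVUS or if automatic pullback was not used for it. A subject leaves the analysis set only if no valid pullback remains.
- **IX.E:** use the same definition, so that a subject with one valid pair is clearly included.
- **VI.B with V.C and V.D:** describe these as exclusions from analysis after enrolment. State that baseline and CCTA/FFRCT data already recorded are kept for excluded subjects, subject to consent.
- **Reporting (IX.B, and the SAP that IX.A announces):** add one table comparing excluded with analysed subjects on the data recorded at enrolment. Word the scope of the agreement claim in its light.

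The cost is a short protocol amendment, slightly more eCRF work for a few subjects, and one table. No new procedure or visit is needed, and no plaque measurements beyond those the workflow already produces.

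### The primary agreement rule in IX.C has no margin or pass fraction and is not the ±36 mm³ limits-of-agreement test that IX.D powers

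*Combined protocol and SAP*

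**What the plan says.** The Synopsis hypothesis is that the automated method "can quantify total plaque volume from CCTA with an acceptable level of agreement with IVUS measurements"; it puts no number on acceptable.

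Section IX.A promises "confidence intervals and hypothesis testing performed for the primary and other selected efficacy endpoints", and leaves detail to a SAP. No SAP text that defines the primary criterion is among the documents.

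Section IX.C gives the only decision rule: "If the deep-learning based automated method CCTA measurements fall with the limits of agreement (LoA) estimated from the IVUS measurements", the "measures will be assumed to agree". Pearson's correlation and a paired t-test are added as further description.

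Section IX.D states that "the maximum allowable difference between the measurements is 36 mm³". "Assuming a standard deviation of 12 mm³", it says that "a sample size of 223 patients achieves 90% power to detect agreement when the mean is 8", with 95% limits of agreement and 95% confidence intervals about them. The 36 mm³ figure appears nowhere else, and IX.C does not refer to it.

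**The concern.** A Bland-Altman analysis supports a claim of agreement only when the limits are compared with a difference fixed in advance as tolerable. IX.C makes no such comparison. It asks whether the measurements fall inside limits that are themselves estimated from study data, and does not say how many must do so. It is also unclear which data produce the limits, since limits of agreement normally come from paired differences and not from one method's measurements.

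Two things are at stake. The primary conclusion could turn on a reading and a cut-off settled after the data are seen. And the sample-size justification belongs to a test that the analysis section never states. IX.C also says that continuous secondary endpoints are compared in a similar way, so the ambiguity may carry over to them.

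**Working it through.** **1. Reproducing IX.D.** Inputs, all from IX.D: margin 36 mm³, SD 12 mm³, mean difference 8 mm³, 95% limits, 95% two-sided CIs. The ± on the margin is inferred.

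- Upper limit: 8 + 1.96 × 12 = 31.52. Lower limit: 8 − 1.96 × 12 = −15.52.
- SE of a limit: SD × √(1/n + 1.96²/(2(n − 1))) = 12 × √(1/223 + 1.96²/444) = 1.375.
- Non-centrality: (36 − 8 − 23.52)/1.375 = 3.26 for the upper limit and (36 + 8 − 23.52)/1.375 = 14.89 for the lower.
- Non-central t power with 222 df: 0.9004 at n = 223 and 0.8991 at n = 222.

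So 223 is exactly the sample size for requiring both CIs to lie inside ±36 mm³. A one-sided bound would need only 182. Direct simulation of the test at 223 gives 0.89. An exact CI for the limits gives 0.856, so the CI method matters.

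**2. IX.C, reading (a): limits from the paired differences.** Normal differences, n = 223, 20,000 simulated trials per case:

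| Bias / SD (mm³) | Mean share inside | Pass if ≥90% inside | ≥95% | ≥97% | All | ±36 mm³ test passes |
|---|---|---|---|---|---|---|
| 8 / 12 | 95.1% | 100% | about 60% | about 2% | 0% | 89% |
| 8 / 60 | 95.1% | 100% | about 60% | about 2% | 0% | 0% |
| 100 / 12 | 95.1% | 100% | about 60% | about 2% | 0% | 0% |
| 100 / 100 | 95.1% | 100% | about 60% | about 2% | 0% | 0% |

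The limits move with the bias and widen with the scatter, so the result reflects only the cut-off.

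**3. Reading (b): limits from the spread of IVUS values.** The documents give no IVUS SD. I assume S = 60, 100 or 150 mm³, with the CCTA error independent of the IVUS value. The share inside is Φ((1.96S − bias)/√(S² + SD²)) − Φ((−1.96S − bias)/√(S² + SD²)).

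| Bias / SD (mm³) | S = 60 | S = 100 | S = 150 |
|---|---|---|---|
| 8 / 12 | 94% | 95% | 95% |
| 8 / 60 | 83% | 91% | 93% |
| 100 / 12 | 61% | 83% | 90% |
| 100 / 100 | 53% | 73% | 84% |

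Large error does lower the share. But CCTA values unrelated to IVUS, with the same mean and SD, fall inside 95% of the time. Their true limits of agreement would be ±1.96 × √2 × S, about ±166, ±277 and ±416 mm³.

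**4. Reading (c): limits from IVUS repeatability.** This could discriminate, but no repeat IVUS reads are described. The reproducibility endpoints in III.B concern repeat CCTA series and repeat processing.

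**5. Reading (d): every individual difference within ±36 mm³.** On the IX.D assumptions each difference is inside with probability 0.990, so all 223 are inside with probability 0.9901^223, about 11%.

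None of the readings that can be calculated gives 90%.

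**6. Several pullbacks per patient.** The endpoint is per pullback and IX.D counts patients. Section V.D, ICA procedure item 6, states that "IVUS data for non-targeted lesions that are standard clinical care will be collected", so a patient may contribute more than one. Assume 223 patients with two pullbacks each and within-patient correlation 0.3, 0.5 or 0.8 (none of these is in the documents). A nominal 95% CI that ignores clustering then covers the upper limit about 93%, 91% and 86% of the time. When the true upper limit is exactly 36 mm³ it passes 4.4%, 5.5% and 8.6% of trials, against 3.7% for independent differences. A patient-level robust CI restores 94–95% coverage.

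**The case against.** The best defence is that the intent can be recovered. The plan does hold a margin: IX.D, which follows directly, gives the tolerable difference, the level of the limits and the level of their CIs, and IX.A promises hypothesis testing for the primary endpoint. Section IX calls itself a brief overview and points to a SAP, which may have fixed the rule before any data were seen.

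Much of this is fair. A margin test was probably meant, and a choice made after seeing the data is a possibility, not something the documents show. It does not rescue the IX.C sentence. A SAP can add detail to a protocol rule, but here it would have to replace the rule with a different one. Correlation and the paired t-test do not fill the gap either: the first measures association, and the second tests for zero mean difference, not agreement within a margin.

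Three limits also stand. The reading (b) figures rest on assumed IVUS SDs and are illustrative. The clustering figures rest on assumptions and are secondary to the main point. The source of the 36 mm³ is not supplied, so its suitability per pullback cannot be checked here.

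**Conclusion.** The concern holds and needs correcting before the primary analysis. The IX.D arithmetic is right, but it belongs to a test that IX.C does not state. Under reading (a) the probability of declaring agreement at n = 223 ranges from 0% to 100% according to an unstated cut-off, and is the same at a bias of 8 or 100 mm³ and an SD of 12 or 100 mm³. Under reading (b) a method carrying no information about IVUS would look as good as an accurate one. The ±36 mm³ test separates these cases, passing 89% of trials on the IX.D assumptions and none in the three poor-agreement cases simulated. The reading (a) result assumes normal, independent differences.

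**What to change.** Replace the IX.C decision sentence with wording such as:

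> Limits of agreement are the mean ± 1.96 SD of the paired per-pullback differences (CCTA minus IVUS). Agreement is declared if the upper bound of the two-sided 95% CI of the upper limit is below +36 mm³ and the lower bound of the two-sided 95% CI of the lower limit is above −36 mm³. Where a patient contributes more than one pullback, the limits and their CIs allow for within-patient clustering (for example, a random patient effect or a patient-level bootstrap).

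Report the mean bias with its 95% CI, name the CI method in the SAP, and keep 223 as a count of patients. The sponsor should confirm that 36 mm³ is meant to apply per pullback and in both directions.

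The cost is one paragraph, carried into the SAP, with no new data items. The real cost is a result that depends on the size of the differences. At n = 223 and mean 8, power falls from 0.90 at SD 12 to 0.68 at SD 12.5, 0.39 at SD 13 and 0.05 at SD 14. On the IX.D assumptions, 250 patients would give 0.93.

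Clustering lowers power below plan only if 223 ends up counting pullbacks. With 223 patients and two pullbacks each, robust-CI power is 0.98, 0.98 and 0.94 at correlations 0.3, 0.5 and 0.8. With 112 patients and two pullbacks each, it is 0.80 at correlation 0.5 and 0.72 at 0.8.
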